7.3.4 Early Termination Visit

Site-specific determination to which of the procedures/evaluations required for the final study visit should be done at a termination visit if early termination occurs and if the participant is willing.

7.3.5 Unscheduled Visit

Site-specific as to how unscheduled visit(s) will be handled and documented.

7.3.6 Schedule of Events Table

Procedures	Study Design / Site Enrollment	Participant Enrollment / Screening / Study Intervention	Baseline assessment / Study Intervention	Follow-up Assessments of Study Endpoints / Safety	Follow-Up Assessment of Study Endpoints / Safety	End of Study Assessments

Recruit and consent study site	X					
Establish site PI and study agreement consent	X					
On-board and train study site personnel	X					
Define site opportunity/channel for participant recruitment	X					
Site-specific study materials from approved IRB submission	X					
Total participants (n=x is site-specific)		X				
Participant mobile app Terms of Use		X				
Obtain informed consent		X				
Screen potential participants by inclusion/exclusion criteria		X				
Obtain history/demographics through Questionnaire		X				
Sample Collection (Study Enrollment or Future Appointment – site-specific)		X	X			
Participant sample sent to Namida Lab, Inc.			X			
Namida Lab, Inc. runs Melody® Assay*			X			
Namida Lab, Inc. returns Melody® assay results to study site			X			
Site clinician/Namida Lab, Inc. review Melody® results (if requested)				X		
Site clinician and study participant review Melody® results				X		
Study participant completes exit Questionnaire					X	
Study personnel completes exit Questionnaire					X	
Namida Lab, Inc. distributes study participant incentive					X	
Ongoing study data analysis at Namida Lab, Inc.		X	X	X	X	
Namida Lab, Inc. completes all data of study endpoints from sites and participants						X
Namida Lab, Inc. closes site/study						X
Access to Future Studies** at Namida Lab, Inc.	X	X			X	

*Melody® Assay is a high complexity lab-developed test that has been developed and validated by Namida Lab, Inc. and will only be run by Namida Lab, Inc.

**Future studies will be offered in a mobile app; participant will need to meet inclusion/exclusion, Re-Consent for a new study

7.4 Concomitant Medications, Treatments, and Procedures

All concomitant prescription medications taken during study participation will be recorded as determined by the site investigator. Prescription medication is a medication prescribed only by a properly authorized/licensed clinician for this protocol. If required by site investigators, medications to be reported are concomitant prescription medications, over-the-counter medications, and non-prescription medications.

Per the exclusion criteria, any woman currently in treatment for breast cancer cannot participate in the VIOLA Study. This includes both local therapy and systemic/adjuvant therapy. Local therapy includes surgery, with or without radiation therapy to the breast and nearby lymph nodes.

Systemic therapy uses drug therapies that travel throughout the body to get rid of cancer cells. It includes chemotherapy, hormone therapy, and HER2-targeted therapy.

8. Assessment of Safety

8.1 Specification of Safety Parameters

Safety is not an endpoint of this study but is a top concern of the sponsor and all site investigators, clinicians, and personnel. There can be a significant experience between participant and clinician when discussing breast cancer screening and screening results. Participant's overall and general well-being is the most significant safety concern; it is site-specific and primarily monitored by the site investigators and the clinical study personnel.

8.1.1 Definition of Adverse Events (AE.)

Adverse event means any untoward medical occurrence associated with the use of an intervention in humans, whether or not considered intervention-related.

8.1.2 Definition of Serious Adverse Events (SAE)

A serious adverse event or serious suspected adverse reaction: An AE or suspected adverse reaction is considered "serious" if, in the view of either the sponsor or principal investigator, it results in any of the following outcomes: death, a life-threatening adverse event, inpatient hospitalization or prolongation of existing hospitalization, a persistent or significant incapacity or substantial disruption of the ability to conduct normal life functions or a congenital anomaly/congenital disability.

Based upon appropriate medical judgment, important medical events that may not result in death, be life-threatening, or require hospitalization may be considered serious when they may jeopardize the participant. This event may require medical or surgical intervention to prevent one of the outcomes listed in this definition.

No examples of a serious adverse event are available for the administration and use of the study assay, Melody®.

8.1.3 Definition of Unanticipated Problems (UP)

Unanticipated problems involving risks to participants or others to include, in general, any incident, experience, or outcome that meets **all** the following criteria:

- Unexpected in terms of nature, severity, or frequency is given (a) the study procedures that are described in the protocol-related documents, such as the IRB-approved clinical utility study protocol and informed consent document; and (b) the characteristics of the participant population being studied; and
- Related or possibly related to participation in the clinical utility study ("possibly related" means there is a reasonable possibility that the incident, experience, or outcome may have been caused by the procedures involved in the study); and
- Suggests that the study places participants or others at a greater risk of harm (including physical, psychological, economic, or social harm) than was previously known or recognized.

8.2 Classification of an Adverse Event

8.2.1 Severity of Event

For AEs not included in the protocol-defined grading system, the following guidelines will be used

to describe severity.

- **Mild** – Events require minimal or no treatment and do not interfere with the participant's daily activities.
- **Moderate** – Events result in a low level of inconvenience or concern with the therapeutic measures. Moderate events may cause some interference with functioning.
- **Severe** – Events interrupt a participant's usual daily activity and may require systemic drug therapy or other treatment. Severe events are usually potentially life-threatening or incapacitating.

8.2.2 Relationship to Study Agent

The site clinician's assessment of an AE's relationship to the study agent (Melody® assay) is part of the documentation process. However, it is not a factor in determining what is or is not reported in the study. If there is any doubt about whether a clinical observation is an AE, the event should be reported. All AEs must have their relationship to the study agent, Melody®, assessed. In a clinical trial, the study agent must always be suspect. To help assess, the following guidelines are used.

- **Related** – The AE is known to occur with the study agent. There is a reasonable possibility that the study agent caused the AE or a temporal relationship between the study agent and event. Reasonable possibility means there is evidence to suggest a causal relationship between the study agent and the AE.
- **Not Related** – There is no reasonable possibility that the administration of the study agent caused the event, there is no temporal relationship between the study agent and event onset, or an alternate etiology has been established.

8.2.3 Expectedness

The sponsor-investigator will be responsible for determining whether an AE is expected or unexpected. An AE will be considered unexpected if the event's nature, severity, or frequency is not consistent with the risk information previously described for the study agent, Melody®.

8.3 Time Period and Frequency for Event Assessment and Follow-Up

The occurrence of an AE or SAE may come to the attention of study personnel during study visits and interviews of a participant presenting for medical care or upon review by a study monitor.

All AEs, including local and systemic reactions not meeting SAEs' criteria, will be captured on the appropriate CRF. Information to be collected includes event description, time of onset, clinician's assessment of severity, relationship to study product/agent (assessed only by those with the training and authority to make a diagnosis), and time of resolution/stabilization of the event.

All AEs occurring while on study must be documented appropriately regardless of relationship. All AEs will be followed to an adequate resolution.

Any medical condition present at the time that the participant is screened will be considered baseline. Baselines are not reported as an AE. However, suppose the study participant's condition deteriorates at any time during the study. In that case, it will be recorded as an AE. UPs will be recorded in the data collection system throughout the study.

Changes in the severity of an AE will be documented to allow an assessment of the duration of

the event at each level of severity to be performed. AEs characterized as intermittently require documentation of onset and duration of each episode.

The site PI will record all reportable events with start dates occurring after informed consent is obtained until seven days (for non-serious AEs) or 30 days (for SAEs) after the last day of study participation. At each study visit, the site investigator or clinician will inquire about AE/SAEs the occurrence of AE/SAEs since the last visit. Events will be followed for outcome information until resolution or stabilization.

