- US Code of Federal Regulations applicable to clinical studies (45 CFR 46)
- ICH GCP E6
- Completion of Human Subjects Protection Training

Protocol Summary

Title: Validating Individualized breast cancer screening by Offering a new Link in Access

Short Title: The VIOLA Study

Précis: The VIOLA Study is a Clinical Utility Study to investigate the useability of Melody®, a tear-based screening assay for breast cancer developed and validated by Namida Lab, Inc., a high complexity CLIA certified lab.

The VIOLA Study will have multiple study sites, with a minimum participation of 205 women who are 40 to 74 years of age, at average risk for developing breast cancer, asymptomatic, and have no concerns or breast abnormalities.

Melody® consists of two parts: tear sample collection and clinical lab assay. Participants will have a tear sample collected at a study site. The clinical lab assay, Melody®, will be performed at Namida Lab, Inc. The results of the Melody® assay will be returned to the site clinician to be discussed with the participant.

Objectives: Primary Objective: Investigate the clinical utility of Melody® in federally qualified health centers in populations with historically low compliance rates with screening mammography.

Secondary Objective: Assess how incorporating Melody® into a primary care provider setting affects participation and confidence in the current breast health continuum of care.

Endpoint: Primary endpoint: The VIOLA Study is designed to quantify the relationship between two variables: an exposure and an outcome, by utilizing different study sites and recruiting from a diverse population.

Secondary endpoint: Quantifying the relationship between Melody® and increased participation in breast health care offers the clinical utility evidence required for adoption into the Standard of Care.

Population: Women ages 40-74 years old, at average risk for developing breast cancer

Number of Sites: 3+ sites

Study Agent: Melody® is a tear-based, high complexity lab-developed test. Melody® has been developed, validated, and will only be run by Namida Lab, Inc. as a tool in breast cancer screening.

Study Duration: 6-12 months

Participant Duration: Six months

Schematic of Study Design

The VIOLA Study: Validating Individualized breast cancer screening by Offering a new Link in Access

Define – Month 1-6 Study Design/Site Enrollment

- Recruit and consent study sites
- Establish study site principal investigator and study agreement consent

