7.1.4 Overall Procedures for Enrolled Participants

After completing the baseline demographics and medical history questionnaires, the participant will schedule a sample collection appointment/walk-in at their study site. The study personnel will collect the tear sample and return it to Namida Lab, Inc. Namida Lab, Inc. will perform the Melody® assay lab-developed test and return the participant's results to their study site. The site clinician will review the Melody® results with the participant.

The participant will receive a notification informing them that the exit questionnaire has been published and is available to complete. Upon completing the exit survey, the participant will be notified that their participation in the study is complete. They will receive instructions to claim the \$25 Walmart gift card.

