8.4.3 Unanticipated Problem Reporting

All possible unanticipated problems will be reported to the IRB within five (5) days of receiving notice of the event if the event requires immediate intervention to prevent serious harm to participants or others.

All other possible unanticipated problems will be reported to the IRB as soon as possible. Reported no later than ten (10) business days from the date of the event or from the date the sponsor-investigator is notified of the event.

Incidents or events that meet the OHRP criteria for unanticipated problems require creating and completing an unanticipated problem report form. The site investigator's responsibility is to report unanticipated problems to the study sponsor, Namida Lab, Inc., for further reporting to the IRB.

The unanticipated problem report will include the following information:

- Protocol identifying information: protocol title and number, PI's name, and the IRB project number.

- A detailed description of the event, incident, experience, or outcome.
- An explanation of the basis for determining that the event, incident, experience, or outcome represents an unanticipated problem.
- A description of any changes to the protocol or other corrective actions taken or proposed in response to the unanticipated problem.

Sponsor-investigator must promptly report (according to the above schedule) the following events to the IRB if the events occur within thirty (30) days of participants' active participation:

- Adverse events, which in the opinion of the sponsor-investigator, are both unexpected and related.
- An unanticipated event related to the utility study that exposes individuals other than the participants (e.g., investigators, research assistants, students, the public, etc.) to potential risk.
- Information that indicates a change to the risks or potential benefits of the utility study.

For example:

- An interim analysis or safety monitoring report indicates that the frequency or magnitude of harms or benefits may differ from initially presented to the IRB.
- A paper is published from another study that shows that the study's risks or potential benefits may be different than initially presented to the IRB.
- A breach of confidentiality.
- Incarceration of a participant in a protocol not approved to enroll prisoners.
- Change to the protocol taken without prior IRB review to eliminate an apparent immediate hazard to a participant.

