10.4.5 Adherence and retention analysis

During the participant's journey through the study, there are various points where adherence and retention can be assessed. A log will be generated for each site listing each participant who has enrolled, their contact information, and where they are in the study process.

1. Study enrollment - A list can be generated by the site of participants enrolled. In addition, participants can be tracked via Namida Lab, Inc.'s LIMS system, as an open order will be generated once the participant's enrollment is complete.
2. Sample collection - Once the participant has completed sample collection at their site, the order will be completed, and the sample received by the lab.
3. Exit survey - A notification method will be arranged by site, which will allow site personnel to alert Namida Lab, Inc. when the results have been reported to study participants. Once this has occurred, the participant will be sent an exit survey.
4. After completing the exit survey, the study participant will receive the \$25.00 Walmart

gift card incentive. This will allow the study sponsor to track adherence and retention.

11. Source Documents and Access to Source Data/Documents

A Case Report Form will be completed for each participant enrolled in the clinical study. The investigator-sponsor will review, approve, and sign/date each completed CRF; the investigator-sponsor's signature serves as an attestation of the investigator-sponsor's responsibility for ensuring that all clinical and laboratory data are entered into the CRF are complete, accurate, and authentic. Any missing or spurious data will be accompanied by a note to file in the participant's record, which will clarify its reason and any action taken afterward.

Source Data are the clinical findings and observations, laboratory and test data, and other information in Source Documents. Source Documents are the original records (and certified copies of original records); including, but not limited to, all consent forms, app screens, app-based screening forms, regulatory documents, hospital medical records, physician or office charts, physician or nursing notes, participant diaries or evaluation checklists, pharmacy dispensing records, recorded data from automated instruments, x-rays, etc. When applicable, information recorded on the CRF shall match the Source Data recorded on the Source Documents.

12. Quality Assurance and Quality Control

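### Non-serious adverse events that are unexpected and related are reportable for 30 days but need be recorded for only 7, and the end of participation that starts the clock is defined in two ways

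*Protocol*

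**What the plan says.** All references are to the Protocol.

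- **Recording window (8.3).** The site investigator records events starting after consent "until seven days (for non-serious AEs) or 30 days (for SAEs) after the last day of study participation". Unanticipated problems are handled separately: "UPs will be recorded in the data collection system throughout the study".
- **Reporting window (8.4.3).** The sponsor-investigator must promptly report a list of events to the IRB "if the events occur within thirty (30) days of participants' active participation". The list includes "Adverse events, which in the opinion of the sponsor-investigator, are both unexpected and related". No seriousness condition is attached.
- **End of participation.** The Protocol Summary has "Participant Duration: Six months". Section 7.1.4 has "Upon completing the exit survey, the participant will be notified that their participation in the study is complete". Section 10.4.5 says when that survey goes out, namely after the site signals that the result has been reported to the participant: "Once this has occurred, the participant will be sent an exit survey".
- **How events are found.** Section 8.3 has the site ask about adverse events at each study visit, and adds contacts for medical care and review by a study monitor as sources. Section 13.6 has the monitor review the medical records of all enrolled participants. Section 8.1 says safety is not an endpoint but ranks the participant's well-being as the leading safety concern, in the context of discussing screening results. Appendix J (participant exit survey) has eleven items. Item 2 rates comfort with the collection. None asks about later eye symptoms, distress or any adverse event. Appendix K item 8 allows the result to be given by phone.

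**The concern.** The recording rule and the reporting rule cover different periods for one class of event. A sponsor can report only what reaches it, and for non-serious events that are unexpected and related the site's recording duty ends well before the sponsor's reporting duty.

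Both rules also depend on when participation ends, and the protocol gives two answers. Two sites could each follow 8.3 in good faith and stop recording at very different times.

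What is at stake is the drawbacks side of a study that section 2.1 describes as weighing usefulness, benefits and drawbacks. Section 2.3.1 lists false-positive results as a risk and puts that rate at 46%. Some consequences of such a result may come after the exit survey: Appendix J item 10 asks whether the woman is going to schedule or complete a mammogram, and item 11 asks to contact her after participation if she plans one.

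**Working it through.** No sample size, power or alpha is involved. The check sets the windows side by side.

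**Step 1. Windows by type of event.** Section 8.4.3 speaks of active participation and 8.3 of the last day of study participation. I assume both count from the same end point.

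| Event | Recorded (8.3) | Reportable as unexpected and related (8.4.3) | Difference |
|---|---|---|---|
| Serious | 30 days | 30 days | 30 − 30 = 0 days |
| Non-serious | 7 days | 30 days | 30 − 7 = 23 days (days 8 to 30) |

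**Step 2. Does the unanticipated-problem route close the gap?** Section 8.1.3 requires all three of: unexpected; related or possibly related; and suggesting a greater risk of harm than previously known. Events meeting all three are recorded throughout the study, and 8.4.3 has the site pass them to the sponsor with no 7-day limit. The adverse-event item in 8.4.3 asks only for the first two properties. What remains is non-serious, unexpected, related events, starting on days 8 to 30, that do not meet the third criterion.

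**Step 3. Is that class empty?** Not evidently. For questionnaires and consultations, 2.3.1 describes only minimal psychological discomfort. Section 8.2.3 makes an event unexpected when its severity does not fit the described risk. Marked but non-serious distress after a High result could be unexpected and related. Whether it also meets the third criterion is a case-by-case judgement.

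**Step 4. The starting point.**

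- Summary reading: participation lasts six months, so non-serious recording runs to six months plus 7 days.
- 7.1.4 and 10.4.5 reading: participation ends when the exit survey is completed, so recording runs to that date plus 7 days. The survey follows the result, but no section dates its completion.

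If the survey is returned soon after the result, the two readings lie months apart. The exact difference cannot be computed. Section 8.3 does not say which reading governs.

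**Step 5. Scale.** If all 205 women were free of cancer, 0.46 × 205 = 94.3, so about 94 would be classified High. This is the number exposed to a false-positive result, not a number of harms or of missed events. The documents give no timing for imaging or biopsy after a High result, so the share of harms starting after day 7 or day 30 cannot be derived.

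**The case against.** The strongest reply is that 8.3 sets active recording while 8.4.3 is a duty to report whatever becomes known, so the two may differ without contradiction. Detection also does not rest on the exit survey alone. Section 8.3 names medical-care contacts and monitor review, 13.6 covers the records of every participant, and 7.3.3 places the exit questionnaire under a final study visit, at which 8.3 requires an inquiry about events. Safety is not an endpoint, and 7.1.5 puts care beyond the consultation outside the study's scope. The consent form is not available here, so the participant's own reporting route cannot be judged.

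Much of this stands, and it keeps the point small. It does not remove it. None of these routes obliges a site to record a non-serious, unexpected, related event starting on days 8 to 30, and none settles when participation ends.

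A reader might go further and infer that harms after a High result fall outside the safety window, or that the study will show few or no harms because of how it is built. The documents do not support that. The survey is sent only after the result is reported, so events between result and survey completion are on study. Non-serious events are then recorded for 7 more days and serious ones for 30. Distress on hearing the result would normally arise inside that period. A reader might also try to date the window in calendar days from the sample report in Appendix I, but that is a test record and says nothing reliable about turnaround in the study. The 30 days in 8.4.1 is a reporting deadline, not an onset window, and adds nothing to the conflict.

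**Conclusion.** The point holds in a narrow form. For non-serious adverse events that are unexpected and related but do not meet all three unanticipated-problem criteria, there are 23 days (days 8 to 30) in which the event is reportable to the IRB but need not be recorded by the site. Serious events are not affected. The end of participation, on which both windows depend, is stated inconsistently, and the exit survey asks nothing about adverse events although the result may be given by phone.

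The conclusion rests on two assumptions: that the 30 days in 8.4.3 run from the same end of participation as the windows in 8.3, and that no removed text defines the last day of participation. The consequence is possible under-capture of later non-serious harms, of a size that cannot be computed from the documents. It is worth correcting because it concerns a safety rule and the repair is cheap. It does not call the study's safety collection as a whole into question.

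**What to change.** 1. In 8.3, have sites record non-serious adverse events that may be unexpected and related through 30 days after the last day of participation, to match 8.4.3. The 7-day limit can stay for other non-serious events. Use the same term for the starting point in both sections.
2. Reconcile the Protocol Summary with 7.1.4 and 10.4.5, and state one definition of the last day of study participation that governs both windows.
3. Add one question to Appendix J on eye symptoms since collection and distress after the result, with any yes sent to the site's adverse-event form.

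The cost is protocol wording, one survey item and a few more event records. A 30-day window for all adverse events counted from six months after collection is not needed. Section 8.3 documents events regardless of relationship, so that would bring in months of unrelated illness, and 13.6 does not say that record review extends that far.
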